2.0	General (Rationale)	NDMA analyses will be based on arithmetic means instead of geometric means. Blinded review of the bioanalytical data revealed that a large number of urine and plasma samples for NDMA were below the lower limit of quantification (LLOQ). For multiple subjects, all samples from 1 or more study periods were below the LLOQ. As zero values cannot be log-transformed for geometric mean analyses, these periods would have been removed from analysis. Furthermore, as analyses are paired, these subjects would have been removed from analyses. Utilizing arithmetic mean will allow data from all subjects and all periods to be used in the planned analysis. Ranitidine and DMA analyses will remain the same (i.e. utilizing geometric means).
	7.3.1	Analysis of urine concentrations Analysis of NDMA urine 24-hr excretion will be performed using arithmetic means instead of geometric means.
	7.3.2	Plasma pharmacokinetics Descriptive statistics for plasma PK parameters of NDMA will be calculated using arithmetic means.

1. Introduction

This document outlines the proposed statistical methods for data analysis of data collected from Protocol ‘SCR-010 Clinical study to investigate the urinary excretion of N-nitrosodimethylamine (NDMA) after ranitidine administration’.

2. Objectives

The following analysis plan provides the framework for the summarization of the data from this study. The analysis plan may change due to unforeseen circumstances but will be finalized prior to database lock. Any changes made after the database lock will be documented and justified in the clinical study report.

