4.2 Exploratory Endpoints

The exploratory endpoints of this study are:

1. AUC from time 0 extrapolated to infinity (AUC_{0-inf}) of plasma ranitidine, NDMA and DMA
2. Cumulative ranitidine and DMA amount excreted in urine over 24 h after ranitidine administration

5. Analysis Populations

The PK population will include all subjects who receive study drug and have at least one on-treatment sample. The safety population will include all subjects who receive at least 1 dose of any of the study drugs. The analysis population will include all subjects in the PK population with sufficient data to calculate PK parameters from at least two study periods of the same meal

type (i.e., low nitrite/NDMA or high nitrite/NDMA). Treatment in all analysis populations will be assigned based upon the treatment which the subjects actually received.

6. Data Screening and Acceptance

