6.1 Handling of Missing and Incomplete Data

The following imputation of missing values will be done:

- PK measurements (urine or plasma) below the quantification limits will be considered equal to zero for all analyses.
- Missing PK data (e.g., skipped plasma sample collected or uncollected urine voids) will not be imputed.

7. General Statistical Considerations

All data will be presented in data listings. Data from subjects excluded from an analysis population will be presented in the data listings, but not included in the calculation of summary statistics.

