7.3.2 Plasma Pharmacokinetics

The following PK parameters will be determined for NDMA, DMA, and ranitidine (only Treatments A and C) for each subject based on all available concentration-time points:

- **AUC from time 0 to the sampling time corresponding to the last quantifiable concentration (C_{last}) (AUC_{0-t})**

AUC_{0-t} will be calculated according to the linear trapezoidal rule from 0 h to the last quantifiable concentration after drug administration.

- **AUC from time 0 extrapolated to infinity (AUC_{0-inf})**

AUC_{0-t} will be extrapolated to infinity from the AUC from time 0 to the sampling time corresponding to the last quantifiable concentration plus the last quantifiable concentration divided by K_{el} , as follows:

$$AUC_{0-inf} = AUC_{0-t} + C_{last}/K_{el}$$

- **Maximum concentration (observed peak drug concentration) (C_{max})**

C_{max} will be read directly from the observed concentrations.

- **Time at which C_{max} occurs (T_{max})**

T_{max} will be read directly from the observed concentrations as the blood sampling time corresponding to C_{max} . The earlier time will be reported in cases where the same C_{max} value is observed for a subject at multiple timepoints

- **Terminal half-life ($t_{1/2}$)**

The terminal half-life will then be calculated using the elimination rate constant as:

$$t_{1/2} = \ln(2)/K_{el}$$

- **K_{el}**

The terminal elimination rate constant, which will be determined from the terminal slope of the log-concentration curve using linear regression

The PK parameters will be analyzed using noncompartmental methods based on actual sampling times. Serum concentrations below the limits of quantification will be set to zero for the purpose of this analysis (see Section 6). AUC_{0-inf} , $t_{1/2}$, and K_{el} for each analyte and subject will only be

included if the subject has 3 or more concentration values on the terminal portion of the pharmacokinetic curve and with an adjusted coefficient of determination (R^2) greater than 0.80.

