AUC_{0-inf} and C_{max} will be compared with either low nitrite/NDMA meals (comparison between Treatments A and B, respectively) or high nitrite/NDMA meals (comparison between Treatments C and D, respectively) using a paired t-test. Normality assumption will be verified using the Shapiro-Wilke test for normality. If the assumption is not valid, the data will be log-transformed, and then tested for normality. Homogeneity of variances will be verified using Lavene's test. If the data in its original or transformed form does not meet the t-test assumptions, a Wilcoxon signed-rank test will be used for the comparison rather than a paired t-test.

These PK parameters will be summarized using descriptive statistics (number of subjects, mean [arithmetic for NDMA; geometric for DMA and ranitidine], SD, coefficient of variation [CV], median, minimum, and maximum) for NDMA, DMA, and ranitidine.

All parameters will be calculated using R software. Mean and individual concentration-time profiles will be presented in graphs.

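### The plasma NDMA endpoint AUC0-inf has no value in a period with every sample below quantification, so its paired ranitidine-placebo test drops those subjects

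*SAP*

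**What the plan says.** SAP 4.2 lists one plasma endpoint: AUC0-inf "of plasma ranitidine, NDMA and DMA". SAP 7.3.2 defines it as AUC0-t plus the last quantifiable concentration divided by Kel, with Kel taken from a regression on log concentration. AUC0-inf, half-life and Kel are only "included if the subject has 3 or more concentration values on the terminal portion of the pharmacokinetic curve", and only if the adjusted R-squared exceeds 0.80.

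Two rules in SAP 6.1 bear on this. The first is "PK measurements (urine or plasma) below the quantification limits will be considered equal to zero for all analyses". The second is "Missing PK data (e.g., skipped plasma sample collected or uncollected urine voids) will not be imputed".

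SAP 7.3.2 compares AUC0-inf and Cmax between treatments A and B and between C and D by paired t-test. If normality fails, a log step follows: "If the assumption is not valid, the data will be log-transformed, and then tested for normality". Then: "If the data in its original or transformed form does not meet the t-test assumptions, a Wilcoxon signed-rank test will be used".

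The change log for version 2.0 says that "a large number of urine and plasma samples for NDMA were below the lower limit of quantification", and that for multiple subjects this covered every sample in one or more periods. It gives this reason for the new NDMA analysis: "Utilizing arithmetic mean will allow data from all subjects and all periods to be used in the planned analysis". For SAP 7.3.2 it lists only a change to the descriptive means.

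**The concern.** The BLQ rule acts on concentrations, but AUC0-inf needs two quantities that a profile of zeros cannot supply. No rule assigns it a value in that case, and a missing value is not imputed. The paired t-test and the Wilcoxon signed-rank test both need both members of a pair. A subject enters the NDMA AUC0-inf comparison only with enough quantifiable NDMA on ranitidine and on placebo. A subject who is quantifiable on ranitidine and entirely BLQ on placebo, potentially the most informative contrast, is left out.

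Version 2.0 was written to stop this kind of loss. It succeeds for urine, where a zero 24-hour amount stays in the arithmetic-mean analysis. It leaves the loss in place for the only named plasma endpoint.

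There is a second gap for Cmax, which is 0 in an all-BLQ period. It keeps the pair on the original scale, but it cannot pass through the log step, and the SAP does not say to skip that step.

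**Working it through.** **1. The SAP's own figure.** SAP 3.2 powers the urine comparison only; no power is stated for plasma. Inputs: ratio 2, CV 100%, one-sided 0.05, 14 completers, 20% dropout.

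- Effect on the log scale: ln 2 = 0.693. SD of the paired log difference: √ln(1 + 1²) = 0.833.
- Noncentrality at n = 14: 0.693 × √14 / 0.833 = 3.11. Power is 90.4%; at n = 13 it is 88.1%.
- 14 / (1 − 0.20) = 17.5, so 18 enrolled.

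The stated figure reproduces.

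**2. The SAP 7.3.2 formulas on low profiles (13 planned samples, 0 to 24 h).**

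| Profile | Cmax | AUC0-t | Last quantifiable value | Kel | AUC0-inf |
|---|---|---|---|---|---|
| All samples BLQ, set to 0 | 0 | 0 | none | undefined (log 0) | none |
| Only 1.2 at 1 h and 1.1 at 1.5 h quantifiable | 1.2 | 0.875 | 1.1 | not allowed (fewer than 3 values) | none |

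For the second row, AUC0-t = 0.5 × (0 + 1.2)/2 + 0.5 × (1.2 + 1.1)/2 = 0.300 + 0.575 = 0.875. Counting substituted zeros towards the three values does not help, because log 0 is undefined and there is still no last quantifiable value in the all-BLQ case. The loss therefore extends beyond all-BLQ periods to those with too few terminal values or a poor fit.

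**3. Pairs lost, simple count.** The documents give no number of all-BLQ plasma periods, so the share p is an assumption.

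| p | Both arms, independent: 18(1 − p)² | Placebo only: 18(1 − p) |
|---|---|---|
| 0.1 | 14.6 | 16.2 |
| 0.2 | 11.5 | 14.4 |
| 0.3 | 8.8 | 12.6 |
| 0.5 | 4.5 | 9.0 |

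**4. Illustration of selection and power.** Simulated lognormal pairs use the SAP 3.2 urine inputs (ratio 2, log-SD 0.833 per period, placebo median 1) and 18 pairs. A period is usable if it exceeds a single threshold, which stands in for the slope rule. With 30/50/70% of placebo periods unusable, 9/20/38% of ranitidine periods are unusable too. The test is Wilcoxon at one-sided 0.05. SAP 7.3.2 states neither side nor level, so these are borrowed from 7.3.1.

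The SD of the log difference is 0.833 × √(2(1 − ρ)). It equals the 0.833 of step 1 at ρ = 0.5 and is 1.177 at ρ = 0. The case consistent with the SAP's power statement is therefore ρ = 0.5; ρ = 0 is a stress case.

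| | ρ = 0.5: 30 / 50 / 70% | ρ = 0: 30 / 50 / 70% |
|---|---|---|
| Pairs kept of 18 | 12.1 / 8.2 / 4.5 | 11.5 / 7.2 / 3.4 |
| Power, all true values | 0.91 | 0.73 |
| Power, kept pairs | 0.70 / 0.49 / 0.15 | 0.36 / 0.20 / 0.03 |
| Power, unusable set to 0 | 0.92 / 0.91 / 0.84 | 0.73 / 0.72 / 0.66 |
| Mean difference, all pairs | 1.41 | 1.41 |
| Mean difference, kept pairs | 1.59 / 1.72 / 1.90 | 1.21 / 1.12 / 1.05 |
| Mean difference, unusable set to 0 | 1.50 / 1.57 / 1.59 | 1.50 / 1.57 / 1.59 |

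Repeat simulations agreed with these power figures to within about 0.04. The paired t-test on the original scale at ρ = 0.5 behaves the same way: 0.87 with all values, 0.67/0.44/0.20 in kept pairs and 0.89/0.88/0.84 with zeros. With 10% of placebo periods unusable, about 16 of 18 pairs remain.

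**5. Direction.** It also depends on the scale. In a closely similar model (correlation about 0.5, threshold at the placebo median), the mean difference among kept pairs rises from 1.42 to 1.76, while the geometric mean ratio falls from 2 to 1.61. With no true effect, the kept-pair difference stays at 0.

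**The case against.** The endpoint is exploratory, and plasma exposure is not left unexamined: Cmax is tested on the same pairs and AUC0-t is summarised. If ranitidine has no effect and the two periods are exchangeable, requiring both to be usable is symmetric, so no inflation of the false-positive rate is shown. The size is illustrative: the change log gives no count and does not say whether the all-BLQ periods were in urine or plasma, and the zero-correlation case does not match the SAP's stated power. The sentence about using all subjects and periods concerns the move away from geometric means; it does not promise that slope-dependent parameters become computable. The Wilcoxon clause can also be read as already covering data that cannot be logged.

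Most of this stands as a limit on importance. The problem is lost power and a selected estimate, not a spurious finding, and the numbers are conditional. None of it supplies a value for AUC0-inf in an all-BLQ period. The uncertain direction does not rest on the zero-correlation case, since step 5 shows difference and ratio moving opposite ways at a correlation of about 0.5. Reading the Wilcoxon clause as covering zeros is sensible, but the SAP should say so.

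Two practical points also stand. Protocol 3.2 and the synopsis name the same endpoint, so an edit to the SAP alone would create a mismatch. AUC0-24 also needs a rule for a missed 24 h sample.

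**Conclusion.** The point holds, and it follows from the SAP's definitions without any simulation. An all-BLQ NDMA period has no AUC0-inf, and its pair leaves both the t-test and the Wilcoxon test, while Cmax on the original scale and urinary excretion keep it. Inclusion then depends on a post-dose outcome.

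The number of pairs lost cannot be derived from the documents. Under the assumptions above it ranges from about 2 of 18 (10% of placebo periods unusable) to more than half (50% or more). In the latter case power at correlation 0.5 falls below one half, where setting the value to zero would hold it at 0.84 or above. These figures rest on assumed unusable shares, a single threshold in place of the slope rule, and urine inputs applied to plasma. The primary analysis is not touched. This should be corrected, but it does not threaten the trial's main conclusion.

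**What to change.** For NDMA only, in SAP 4.2 and 7.3.2:

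- Compare AUC0-24 instead of AUC0-inf: linear trapezoid over the planned 0 to 24 h samples at actual times, BLQ set to zero, so that an all-BLQ period counts as 0. It has to be specified separately, because AUC0-t stops at the last quantifiable sample.
- State what happens if the 24 h sample is missing. Leaving AUC0-24 missing and counting it as such would fit SAP 6.1, and that loss would not be caused by a low NDMA level.
- Report AUC0-inf descriptively, with the number of evaluable pairs for A-B and for C-D.
- For AUC0-24 and Cmax, omit the log-transform step and go straight to the Wilcoxon signed-rank test if the t-test assumptions fail.

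Keep AUC0-inf for ranitidine and leave DMA unchanged. Add a matching note for Protocol 3.2 and the synopsis.

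The cost is wording and one extra AUC per period, with no new samples. There are three drawbacks. Exposure after 24 h is left out. Setting BLQ to zero itself moves the mean difference (1.41 to about 1.50-1.59 in the illustration). Pairs at zero in both periods add nothing to the Wilcoxon test.

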### **4.9.6 Pharmacokinetic Analysis**

#### **4.9.6.1 Urine Pharmacokinetics**

Cumulative amount of NDMA (primary), DMA (exploratory), and ranitidine (exploratory) excreted in urine over 24-h for placebo and ranitidine administration will be calculated for each

subject. All urine over a 24-h period will be collected. Each separate void will be weighed in a tarred container. The volume of the void will be determined assuming a specific gravity of 1.01. Concentration of each collected sample will be used to determine a cumulative amount excreted as follows:

$$Ae_{0-24} = \sum^{\text{time}} \text{Urine}_{\text{weight,time}} * 1.01 * \text{Conc}_{\text{urine,time}}$$

For both NDMA (primary), DMA (exploratory) and ranitidine (exploratory) measures will be log-transformed and utilize a mixed-effect analysis of variance (ANOVA) approach for comparing geometric means with terms for treatment, period, and sequence as fixed effects. The results will be transformed back to the original scale by exponentiation to provide treatment geometric means. Testing will be one-sided and a significant increase will be concluded if the lower bound of the one-sided 95% interval for the geometric mean ratio excludes 1.

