#### **4.9.6.2 Plasma Pharmacokinetics**

The PK parameters  $AUC_{0-\text{inf}}$ ,  $C_{\text{max}}$ ,  $AUC_{0-t}$ ,  $T_{\text{max}}$ , and  $K_{\text{el}}$  will be summarized for NDMA, DMA, and ranitidine using descriptive statistics (number of subjects, mean, SD, coefficient of variation [CV], median, minimum, and maximum) for both treatment groups. The PK parameters will be analyzed using noncompartmental methods based on actual sampling times. All parameters will be calculated using SAS or R software. Mean and individual concentration-time profiles will be presented in graphs. Calculation of PK parameters will be performed using actual sampling times.

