3.1 Study Design

This is a randomized, placebo-controlled, single-dose, 4-period crossover study with 18 healthy subjects. Subjects will receive 4 treatments over the 4 study periods (see Table 1). Each subject will be randomized to 1 of 4 treatment sequences (i.e., ABCD, ABDC, BACD, or BADC). The treatment will consist of oral administration of either a single dose of ranitidine (300 mg) or placebo administered at time zero on each of 4 different treatment days. All subjects will be provided low nitrite/NDMA meals for the first 2 periods of the study and high nitrite/NDMA meals for the last two periods of the study. Subjects will check in on Day -2 for baseline assessments and will complete each 2-day period over the next 8 days, followed by checkout (see Table 2).

Two different full day menus of low nitrite/NDMA and high nitrite/NDMA meals have been developed. Meals will be identical for treatment periods 1 and 2 (low nitrite/NDMA meals) of the study and a separate set of identical low nitrite/NDMA meals will be served on the washout days prior to treatment. Likewise, meals will be identical for treatment periods 3 and 4 (high nitrite/NDMA meals) and a separate set of identical high nitrite/NDMA meals will be served on the washout days prior to treatment days. The last meal on Day -1, Day 2, Day 4, and Day 6 should be administered at approximately 6 PM to permit at least 12-hour fasting prior to dosing. Subjects will be provided with distilled water to drink throughout the study.

On study treatment days, the first meal will be provided at the time of dosing. Subjects will be instructed to swallow the medication with approximately 250 mL of room temperature distilled water and begin eating within two minutes after dosing. Subjects are required to eat each meal in its entirety during the study. If the meal is not finished, the reason should be recorded, along with what was not eaten, and a picture of the remaining food should be taken.

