Cumulative amounts of DMA and ranitidine will be log-transformed. A mixed-effect analysis of variance (ANOVA) approach will be used for comparing arithmetic means (for NDMA) and geometric means (for DMA and ranitidine) looking at the effects of treatment, period, and sequence. For NDMA, testing will be one-sided at a 0.05 significance level, and a significant increase will be concluded if the lower bound of the one-sided 95% interval for the arithmetic mean difference excludes 0. For DMA and ranitidine, testing will be one-sided at a 0.05 significance level, and a significant increase will be concluded if the lower bound of the one-sided 95% interval for the geometric mean ratio excludes 1. The results will be transformed back to the original scale by exponentiation to provide treatment geometric means.

Normality assumption of the ANOVA will be verified using the Shapiro-Wilke test for normality and homogeneity of variances will be verified using Levene's test. If either assumption is not valid, a Wilcoxon signed-rank test will be used for the comparison rather than an ANOVA.

Individual and mean time course plots of NDMA, DMA, and ranitidine excreted over 24-hr will be evaluated for each treatment. All urine PK parameters will be summarized using descriptive statistics (number of subjects, mean, SD, coefficient of variation [CV], median, minimum, and maximum) for NDMA, DMA, and ranitidine. Individual time course plots will use actual sampling times. Treatment mean plots will use planned sampling times.

All calculations and the hypothesis testing will be done using R software.

Total fraction of the ranitidine dose excreted in urine ($Fe_{0-24, \text{ranitidine}}$) will be determined for Treatments A and C based on the cumulative amount of ranitidine excreted in urine over 24-h ($Ae_{0-24, \text{ranitidine}}$) divided by 300 mg. This will be calculated for each individual, summarized using descriptive statistics (number of subjects, mean, SD, CV, median, minimum, and maximum), and visualized graphically using box-and-whisker plots.

Renal clearance of ranitidine will be determined (only for Treatments A and C) by calculating the rate of excretion as the difference between the later and earlier compound level divided by the difference in times points (i.e., $[\text{amount}_{t_2} - \text{amount}_{t_1}] / [t_2 - t_1]$). The log-transform of the renal

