9.1 Randomization schedule

This is a 4-period, double-blind, crossover study where approximately 18 subjects will be enrolled to receive either ranitidine or placebo administered with meals from a pre-specified menu with foods that are either low or high in nitrites and NDMA. Subjects will be randomized to one of four treatment sequences (i.e., ABCD, ABDC, BACD, or BADC), where treatment codes are summarized in the table below. The sequence randomization is set so that all subjects will be provided low nitrite/NDMA meals for the first two periods of the study and high nitrite/NDMA meals for the last two periods of the study. The first 16 subjects to get enrolled will be randomized in blocks of 4. The remaining two subjects will be randomly placed in 2 of the 4 treatment sequences. The study plans for 1:1 enrollment of males and females, but the randomization will not account for sex and treatment sequence interactions.

Table 3: Treatment Codes and Treatment Names

Treatment Code	Treatment Name
A	Ranitidine (300 mg) + low nitrite/NDMA meals
B	Placebo + low nitrite/NDMA meals
C	Ranitidine (300 mg) + high nitrite/NDMA meals
D	Placebo + high nitrite/NDMA meals

10. References

Zeng T and Mitch WA. 'Oral intake of ranitidine increases urinary excretion of N-nitrosodimethylamine' *Carcinogenesis* 2016 Jun; 37(6): 625-34

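### The plasma NDMA and DMA comparisons ignore period, although drug order is randomised and the urine model in the same SAP adjusts for it; the cost depends on a period effect that the documents do not quantify.

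*SAP*

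**What the plan says.** **Plasma.** SAP 7.3.2 compares AUC0-inf and Cmax for A versus B and, in the same sentence, specifies a "comparison between Treatments C and D, respectively) using a paired t-test". If the assumptions fail even after log transformation, "a Wilcoxon signed-rank test will be used for the comparison rather than a paired t-test". No period or sequence term appears, and no sidedness is stated. Ranitidine is determined only in treatments A and C, so the tests concern NDMA and DMA. Protocol 4.9.6.2 names no plasma test; it plans summaries "using descriptive statistics (number of subjects, mean, SD, coefficient of variation [CV], median, minimum, and maximum) for both treatment groups".

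**Urine.** For the same subjects and periods, SAP 7.3.1 uses a mixed-effect ANOVA "looking at the effects of treatment, period, and sequence". Protocol 4.9.6.1 gives the same model, "with terms for treatment, period, and sequence as fixed effects".

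**Order.** SAP 3.1: "Each subject will be randomized to 1 of 4 treatment sequences (i.e., ABCD, ABDC, BACD, or BADC". Whether ranitidine or placebo comes first is therefore randomised within the low-meal pair (periods 1 and 2) and within the high-meal pair (periods 3 and 4). SAP 9.1 on allocation: "The first 16 subjects to get enrolled will be randomized in blocks of 4", then "The remaining two subjects will be randomly placed in 2 of the 4 treatment sequences".

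**The concern.** In a randomised crossover, a difference between the two periods enters each subject's ranitidine-minus-placebo difference with a plus sign in one order and a minus sign in the other. A paired test treats that as noise. If the two orders are unequal in number, the shift does not cancel and moves the estimate.

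The two periods of a pair are not fully alike. Treatment-day meals are identical within a pair, but the washout-day meals are of the same type as the treatment day that follows (SAP 3.1). Periods 1 and 3 therefore follow one day on the menu type, and periods 2 and 4 follow three. The SAP gives no reason for adjusting urine but not plasma. What is at stake is some precision in the plasma comparisons, some error in their estimates if pairs are lost unevenly, and the chance that urine and plasma differ through method alone.

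**Working it through.** **1. The plan's own figure.** No sample-size figure is given for plasma. The urine figure in SAP 3.2 (geometric mean ratio 2, CV 100%, one-sided 0.05, 14 completers, at least 90% power) can be reproduced with a paired t-test on the log scale:
- effect = ln 2 = 0.693
- SD of the paired log difference = sqrt(ln(1 + 1²)) = 0.833, reading the CV as that of the paired ratio
- power from the noncentral t distribution = 0.904 at n = 14, the smallest n that reaches 90%
- 14 / 0.8 = 17.5, rounded up to 18 enrolled.

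**2. Model for the check.** Let d = δ + s·π + error. Here d is ranitidine minus placebo for one subject, s is +1 or −1 by order, and π is the difference between the two periods of the pair, in units of the SD of d. The unadjusted analysis is the one-sample t-test on d (n − 1 df). The adjusted analysis takes the mean of the two order-group means (n − 2 df). Assumptions: the values of π, because the documents give none; one-sided 0.05; and two effect sizes, the urine planning value 0.693 / 0.833 = 0.83 SD and a smaller 0.7 SD.

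**3. Precision at 9:9 (n = 18).** The paired standard error is inflated by sqrt(1 + π²·18/17), which is 1.03, 1.12 and 1.43 at π = 0.25, 0.5 and 1 SD. Simulated power, unadjusted versus adjusted:

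| π (SD) | Effect 0.83 SD | Effect 0.7 SD |
|---|---|---|
| 0 | 95.9% vs 95.8% | 88.7% vs 88.6% |
| 0.25 | 95.3% vs 95.8% | 87.4% vs 88.4% |
| 0.5 | 93.6% vs 95.9% | 84.1% vs 88.5% |
| 1 | 84.0% vs 95.7% | 68.2% vs 88.3% |

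The losses are about 0.5 to 1 point, 2 to 4 points, and 12 to 20 points. On the urine planning scale, π = 0.5 SD is a period ratio of exp(0.5 × 0.833) = 1.52, and π = 1 SD is exp(0.833) = 2.30.

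**4. Order split as randomised.** Assume that each block of 4 holds each sequence once. The first 16 subjects then give 8:8 in each meal type. The last two take two different sequences, so there are six possible pairs:
- A/B order becomes 10:8 or 8:10 for {ABCD, ABDC} and {BACD, BADC}.
- C/D order becomes 10:8 or 8:10 for {ABCD, BACD} and {ABDC, BADC}.
- Both stay at 9:9 for the other two pairs.

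Each test is thus unequal in 2 of 6 placements.

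**5. Shift of the estimate** = π × (n1 − n2) / (n1 + n2):
- 9:9 gives 0
- 10:8 gives 2/18 = 0.11π
- 9:5 gives 4/14 = 0.29π

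**6. Why the split could become more unequal.** SAP 7.3.2 keeps AUC0-inf only with at least three terminal-phase values and adjusted R² above 0.80. The SAP change log reports many NDMA samples below the LLOQ and, in multiple subjects, whole periods below it. After random loss from 9:9, the average absolute imbalance is 0.10 with 14 pairs and 0.20 with 8 (95th percentiles 0.29 and 0.50). At 9:5 with π = 0.5 SD, the one-sided type I error of the paired test is 9.5% or 1.0%, depending on the direction of the shift, against 5% adjusted.

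**7. Price of adjusting when π = 0.** It is about 0.1 to 0.3 power points in balanced sets, and 90.4% versus 87.9%, about 2.4 points, at 9:5.

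**The case against.** The strongest reply is that a period effect is only possible. The change from low to high meals falls between periods 2 and 3, outside both comparisons. Nothing in the documents shows that one rather than three days on a menu moves plasma NDMA or DMA. A reader might infer that the design makes a loss of precision certain; the documents do not support that. The 1 SD row in particular assumes a period ratio of 2.30, larger than the 2-fold drug effect in the sample-size calculation.

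A reader might also infer systematic bias. Before any loss of subjects, 10:8 and 8:10 are equally likely, so the unadjusted estimate is unbiased over the randomisation. The shift belongs to the allocation actually realised and is at most 0.11π. Nor is the imbalance found in 4 of 6 placements for a given test; that count takes the two meal types together. At 9:9 the paired test errs towards caution, with type I error about 3.5% at π = 0.5 SD.

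The contrast with urine is also less clean than it looks. If its assumption checks fail, SAP 7.3.1 too falls back to an unadjusted signed-rank test, and the many NDMA values set to zero make that plausible. Finally, AUC0-inf is an exploratory endpoint and Cmax is not among the listed endpoints.

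All of this stands and limits the size of the point. It does not give a reason to leave out a term that the randomised order supports. The remark in Protocol 4.1 that the chosen sequences affect only the between-meal comparison concerns the fixed meal order, not periods within a pair.

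**Conclusion.** The point holds as a minor, conditional one. The planned plasma tests ignore period where the design allows adjustment and the urine ANOVA makes it. If there is no period effect, nothing is lost. If there is one, the loss at 9:9 is negligible at 0.25 SD, modest at 0.5 SD, and large only at a shift that would be surprising. Error in the estimate is small as randomised. It matters mainly for NDMA AUC0-inf, where lost periods could leave few and unevenly ordered pairs and move the type I error in either direction.

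These sizes rest on assumed period shifts, on normal differences, on urine planning values or a 0.7 SD effect applied to plasma, and on one-sided 0.05, which SAP 7.3.2 does not state. They describe the t-test, not the rank fallback. The primary urine conclusion is not affected.

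**What to change.** In SAP 7.3.2, analyse each meal type as a two-period crossover: treatment, period and sequence (drug order within the pair) as fixed effects, and subject as a random effect. Replace the signed-rank fallback with a rank-sum test that compares the within-subject period differences (second period minus first) between the two orders. The period effect is common to both orders and drops out.

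Do not simply copy the urine text, because its signed-rank fallback has the same gap; the same replacement would serve in SAP 7.3.1. State the sidedness of the plasma tests; this point does not depend on which is chosen. Report the number of pairs in each order for every comparison. If the paired test is kept, give the reason for treating plasma differently from urine.

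The cost is SAP wording, reuse of the urine code and one degree of freedom (17 to 16 with 18 pairs), plus the small power cost shown above if no period effect exists.
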